Every effort will be made to ensure adherence by patients, their family and study personnel. This includes inclusion of all eligible patients, accession of initial data in a timely fashion and prompt institution of CBZ treatment. Data sheets will be used to record every step in the protocol including enrollment, collection of initial clinical and lab data, data transmission and initiation of CBZ treatment. Patients will be seen at 4 weeks (+/- 1 week) following initiation of study product and then again at 8 weeks (+/-2 weeks), 18 weeks (+/- 2 weeks), 36 weeks (+/-2 weeks) and finally at the week 52 visit(+3 weeks), which will include the repeat HVPG measurement and liver biopsy.

These visits will involve history, physical exam, pill counts and lab tests to monitor each of the clinical and biochemical parameters mentioned above (refer to Study Flow Chart in Appendix 2). In addition serum levels of CBZ will be measured at each follow- up visit. All data will be recorded on the patient flow log.

OVERALL PATIENT MANAGEMENT

This study will generally not affect patient management, although there will be minor modifications made related to the HVPG measurements. Medications known to influence HVPG measurements (e.g. nonspecific beta blockers) will be discontinued for 3 days prior to HVPG measurements. Each of the subjects is being followed for supportive management of severe liver disease. This will include careful monitoring and medical therapy as indicated by the responsible physician team. At the end of the study period a follow-up HVPG measurement will be performed accompanied by transvenous liver biopsy. As with the first procedure, medications known to influence HVPG measurements will be discontinued for 3 days prior to the procedure. If the subject undergoes liver transplantation during the study period, tissue from the native liver will be collected immediately upon its removal for the analyses proposed above. Follow up HVPG measurements will not be performed in these patients.

PATIENT WITHDRAWAL

It is the right of the patient, the patient's parents or legal guardians, or the physicians caring for the patient to discontinue study medication at any time during the study. Medical care and transplantation will proceed in a manner that is unaffected by study participation.

COMPLETE LIST OF WITHDRAWAL CRITERIA

1. Child-Pugh score >12.
2. Hepatic encephalopathy uncontrolled with outpatient medical therapy.
3. Total bilirubin >7 mg/dl.

A Preliminary Study of the Efficacy and Safety of Carbamazepine in Severe Liver Disease Due to Alpha-1 Antitrypsin Deficiency

4. Evidence of anticonvulsant hypersensitivity syndrome.
5. Leukocyte count <1,000 despite 2 weeks of CBZ dose reduction.
6. Neutrophil count <500 despite 2 weeks of CBZ dose reduction.
7. Platelet count <20,000 despite 2 weeks of CBZ dose reduction.
8. Hemoglobin <8.5 mg/dl.
9. INR greater than or equal to 2.5 not corrected by vitamin K 5 mg.
10. ALT >750 IU/L.
11. Pregnancy.
12. Breast feeding.
13. Evidence for behavior or ideation predisposing to suicide or increase in C-SSRS score of 1 from previous test score.
14. Persistent non-adherence to medication study regimen.

DATA RETRIEVAL AND STORAGE

A data repository in the University of Pittsburgh computing facility has been established to accept all information about subjects including; demographics, history, physical exam, labs and a tracking/event file. The tracking/event file is designed for important events: study entry; study completion; adverse events; treatment failures; exits; dropouts; protocol violations; etc. Security of the deposited data will be maintained through the use of unique patient identifier numbers and passwords to enter the repository. Data can be exported from the repository for reporting and statistical analysis.

Data quality and accuracy will be audited annually by comparing what is in the database with the medical records of the patients.

The electronic data storage and retrieval system used for the purpose of this clinical investigation has not been fully validated for compliance with the FDA regulations at 21 CFR Part 11 taking into account the limited size and scope of the investigation.

DATA AND SAFETY MONITORING PLAN

The Data and Safety Monitoring Board (DSMB) will consist of individuals who are independent of the institutions and investigators participating in the CBZ study, and who have no financial ties to the outcome of the trial. The ongoing review of the data by this independent committee assures the investigators and the study sponsor that the trial can continue without jeopardizing patient safety. Individuals on the DSMB will be responsible for monitoring data and safety during the course of this study.

The DSMB will review the study protocol, recommend recruitment continuation, monitor all aspects of the study (e.g., recruitment, protocol deviations, adverse events, site visit summaries, data quality, attrition, descriptive characteristics), and recommend protocol modifications, which may include early study termination. Annual reports will be prepared by the study investigators including tables showing study progress overall and including recruitment, protocol deviations, attrition, adverse events, and data quality. There will also be a table providing descriptive characteristics of the study sample. The study investigators

A Preliminary Study of the Efficacy and Safety of Carbamazepine in Severe Liver Disease Due to Alpha-1 Antitrypsin Deficiency

will maintain a cumulative summary of adverse events overall and stratified by serious/non-serious status to be forwarded to the DSMB biannually. The DSMB will meet at least once per year in person or via internet conferencing. A closed session will be held to review safety, efficacy, and data quality. Based on the data presented, the DSMB will recommend continuation, changes, or termination of the study. A summary of the DSMB findings will be forwarded to all investigators for submission to the IRB.

The DSMB will meet at least annually in person or via internet conferencing to evaluate the following issues:

1. Progress of the study, including assessment of data quality and timeliness.
2. Subject recruitment, accrual and retention.
3. Review of outcomes and adverse events to determine whether there has been a change in the risk-benefit ratio of the study and whether the study should continue as originally planned, should be changed or terminated.
4. Assessment of external factors such as relevant information from the current literature, including therapeutic developments and results of related studies, that could have an impact on safety of participation in the study or ethics of the study.
5. Review of study procedures to protect the privacy of the research subjects and confidentiality of their research data.

The following information will be reported by the DSMB to the investigators for submission to the IRB at regular annual intervals:

1. The date(s) and frequency of the DSMB meetings.
2. Summary of cumulative adverse event data including a respective assessment of whether the events were caused by the experimental intervention.
3. Summary of the assessment of relevant information from the current literature that could have an impact on safety of participation in the study or ethics of the study.
4. Summary of the outcome of procedural reviews carried out to ensure subject privacy and confidentiality of research data.
5. Final conclusions regarding changes to the benefit-to-risk ratio of study participation and final recommendations related to continuing, changing or terminating the study.
6. Rationale for any recommended changes in the research study protocol.
7. The study investigators are committed to comply with IRB policies for reporting of serious and unexpected adverse events, disputes between investigators and research subjects, and disputes between investigators as articulated in chapters 3.0, 3.4 and 3.5 of the IRB Reference Manual. The study investigators are also committed to monitoring of data for accuracy and protection of subject confidentiality. This monitoring will be carried out by the study coordinator. The study coordinator will also audit all regulatory documents. The investigators and study coordinator will conduct quarterly meetings to review study data and confidentiality. Minutes from these meetings will be kept in the study regulatory binder.

INSTITUTIONAL REVIEW BOARD REQUIREMENTS

A Preliminary Study of the Efficacy and Safety of Carbamazepine in Severe Liver Disease Due to Alpha-1 Antitrypsin Deficiency

The protocol will be approved by the University of Pittsburgh IRB.

INFORMED CONSENT

Written informed consent from the patient, parent or legal guardian is required for any part of this study. The consent form will embody the legally required elements of informed consent. The investigative team shall give the patient or his/her representative adequate time to read the form prior to signing. A copy shall be given to the person signing the form. The patient, parent or legal guardian can withdraw from the study at any time and this decision will not influence the treatment otherwise offered. The NIH guidelines on inclusion of females and minorities as subjects in clinical research will be followed.

CONTRACTUAL ARRANGEMENTS

None yet.

REIMBURSEMENT OF SUBJECTS

If subjects need financial assistance to cover travel expenses for participation in the study, funds will be provided in the following amounts: up to \$500 if they live within 100 miles of Pittsburgh; up to \$3,000 if they live 100-500 miles away from Pittsburgh; up to \$5,000 if they live 500-1,000 miles away from Pittsburgh; up to \$7,000 if they live more than 1,000 miles from Pittsburgh, and up to \$10,000 if they live more than 1,300 miles from Pittsburgh. When airfare from certain locations exceeds these amounts, we may provide an amount of funding that covers the airfare and other travel costs [for the subject and an accompanying adult \(parent\(s\), spouse, etc.\)](#) even if it exceeds the amounts mentioned above.

SUMMARY

A Preliminary Study of the Efficacy and Safety of Carbamazepine in Severe Liver Disease Due to Alpha-1-Antitrypsin Deficiency

Aim of project: The primary objective is to determine if CBZ therapy in patients with severe liver disease due to AT deficiency leads to a significant reduction in the hepatic accumulation of ATZ globules

1. **Criteria for Inclusion:** Subjects must have clinical or histologic evidence of compensated cirrhosis secondary to a diagnosis of homozygous PIZZ or PISZ AT deficiency confirmed by PI typing and serum AT levels (in subjects who are receiving AT replacement therapy at the time of enrollment, AT deficiency will be confirmed by ZZ or SZ phenotype and serum levels <83 mg/dl at the time of initial diagnosis and/or prior to the initiation of AT replacement therapy). Subjects must be able to tolerate oral medication. Age ≥ 14 to ≤ 80 years of age. Inclusion of nonpregnant females and minorities will follow NIH guidelines.

Criteria for Exclusion: Subjects will not be excluded on the basis of gender, race or ethnic group. Subjects will be excluded if they have a history of bone marrow depression, hypersensitivity to carbamazepine or any of the tricyclic compounds such as amitriptyline, desipramine, imipramine, protriptyline or nortriptyline.

A Preliminary Study of the Efficacy and Safety of Carbamazepine in Severe Liver Disease Due to Alpha-1 Antitrypsin Deficiency

Subjects will be excluded if they have evidence of an additional potential cause of active liver disease (e.g. infectious hepatitis, alcohol related liver disease, Wilson disease, sclerosing cholangitis, primary biliary cirrhosis). Subjects will also be excluded if they have very severe liver disease (Child-Pugh score greater than or equal to 12; serum bilirubin > 5; INR > 2.2; hepatic encephalopathy uncontrolled with outpatient medical therapy), severe renal disease (serum creatinine > 1.5 mg/dl), alcohol intake > 30 gms/day, evidence of hepatobiliary malignancy, pregnancy/lactation, portal vein or splenic vein thrombosis, severe cardiac or pulmonary disease felt to be a contraindication to CBZ therapy, HLA-B*1502-positivity, HLA-A*3101-positivity, history of suicide attempt, potential for suicide behavior based on pre-treatment screening test, severe leucopenia (wbc count < 1,500) or thrombocytopenia (platelet count < 25,000).

Total Duration of Therapy: 12 months

Forms to Complete: Informed consent signed by patient and or parent/legal guardian; entry data; visit follow up data; final report

Endpoints of the study:

1. Change in hepatic load of ATZ.
2. Change in degree of hepatic fibrosis.
3. Change in HVPG.
4. Ability to tolerate long-term course of CBZ without adverse events.

Reimbursement for study participation: Only financial assistance to cover travel related expenses.

A Preliminary Study of the Efficacy and Safety of Carbamazepine in Severe Liver Disease Due to Alpha-1 Antitrypsin Deficiency

Literature Cited

1. Perlmutter D.H., Alpha-1-Antitrypsin Deficiency, in Schiff's Disease of Liver, Schiff E.R., Maddrey W.C., Editor. 2007; Lippincott-Raven: Philadelphia. 1063-1084.
2. Perlmutter, D.H., Pathogenesis of chronic liver injury and hepatocellular carcinoma in alpha-1-antitrypsin deficiency. *Pediatr Res*, 2006; **60**: 233-8.
3. Perlmutter D.H., Autophagic disposal of the aggregation-prone protein that causes liver inflammation and carcinogenesis in alpha-1-antitrypsin deficiency. *Cell Death Differ*, 2009; **16**: 39-45.
5. Sveger T., Liver disease in alpha1-antitrypsin deficiency detected by screening of 200,000 infants. *N Engl J Med*, 1976; **294**: 1316-21.

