The primary efficacy outcome will be to determine the effect of CBZ on hepatic ATZ load. This will be based on the number of hepatocytes with PAS+/diastase-resistant globules. Secondary measures will include the area of a liver section occupied by these globules. If there is enough tissue available for immunoblot analysis we will also use the steady state level of ATZ as a measure of hepatic ATZ load. For the secondary efficacy outcomes we will determine the effect of CBZ treatment on hepatic fibrosis on the basis of Sirius red staining and hydroxyproline concentration and whether CBZ treatment changes portal pressure as determined by HVPG. We will also determine if CBZ treatment reduces the MELD score by monitoring it at the beginning and end of the 12-month treatment period, including measuring at 7 follow-up visits while on active medication or placebo. The differences in the change in MELD score for subjects on active medication will be compared to that in subjects on placebo. Safety and tolerability will be investigated by close observation and routine laboratory testing of the 30 subjects.

A Preliminary Study of the Efficacy and Safety of Carbamazepine in Severe Liver Disease Due to Alpha-1 Antitrypsin Deficiency

STUDY POPULATION

Potential subjects for the study will be identified from the clinical practices of the pediatric and adult hepatology programs in the UPMC system and via outside referrals. The typical potentially eligible subject will have AT deficiency (ZZ and SZ phenotypes and low serum level) and clinical evidence of cirrhosis complicated by portal hypertension (e.g. splenomegaly or thrombocytopenia [platelet count <150,000 or a complication of portal hypertension (e.g. varices or ascites)]. HVPG measurement will be used as a screening procedure to determine if the potential study subject has documented significant portal hypertension (HVPG greater than or equal to 10 mm Hg or as indicated in inclusion criteria below). The research program will be advertised in relevant specialty journals and through the Alpha-1 Association. Interested individuals would need to be seen in the aforementioned clinical programs. Eligible subjects will be approached by one of the study investigators so that the study can be explained and inclusion/exclusion criteria can be reviewed.

SCREENING

Following a signed assent/consent, patients with AT deficiency will undergo a screening assessment to determine their eligibility for the interventional study.

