During therapy, study subjects will be seen on a regular basis to assess their clinical status and to obtain standard biochemical measures of liver and renal function, cell counts, etc. Visits will also include a full history and physical examination. Specific assessments and queries will be made for any signs or symptoms of liver disease. Child-Pugh (CP) score and MELD score will be calculated at each study visit. Other than blood collection during study visits, no additional invasive testing is proposed until the week 52b visit when a repeat liver biopsy and HVPg will be obtained. The procedure for the liver biopsy and HVPg will be identical to the procedure used in the screening visit. Data will be collected from procedures undertaken as part of clinical follow up (e.g. endoscopy reports, imaging studies, etc.).

If the study subject undergoes liver transplantation during the study period, samples will be obtained at the time of surgery to provide follow up data. If a subject dies during the study period and the family consents to an autopsy, samples of liver tissue will be obtained at autopsy to provide follow up data. In these cases, follow up HVPg measurements will not be available.

Potential for suicide attempts will be monitored with the Columbia Suicide Severity Rating Scale (C-SSRS) at study visits the week of enrollment through week 52a. It is a semi-structured, clinician-administered instrument to track severity of both suicidal behavior and ideation. This measure is reliable and valid and has been used in previous clinical trials (44, 45). Patients will be withdrawn from the trial if the C-SSRS identifies suicidal ideation or behavior and then the patient will then be referred for mental health evaluation and treatment.

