Study visits will be scheduled at weeks 4 (+/- 1 week), 8 (+/- 2 weeks), 18 (+/- 2 weeks), 36 (+/- 2 weeks), and 52a (+ 3 weeks) for a history and physical examination, assessment for depression and suicide behavior, biochemistry measures, and measurement of the blood level of the CBZ. Blood will also be collected at the time of enrollment and at week 52 visit for Fibrotest analysis. All female subjects of child-bearing age will undergo a urine pregnancy test on visit S2, enrollment, and at each follow up visit during the trial. The effect of CBZ treatment will also be assessed by a novel investigative test, a hepatic biomarker assay using samples that are obtained pre- and post-treatment as well as once during treatment. Study subjects may undergo MRI using Elastography within the first six months of study enrollment and at week 52 visit.

Additional visits may be scheduled, at the discretion of the Investigator, to ensure the safety and well-being of subjects. These will include a history, assessment for depression and suicide behavior, biochemistry measures, and measurement of the blood level of the CBZ. A physical exam may also be performed at the discretion of the investigator. Full list of assessments can be found on the schedule of events flow sheet.

A Preliminary Study of the Efficacy and Safety of Carbamazepine in Severe Liver Disease Due to Alpha-1 Antitrypsin Deficiency

Assessment of adherence:

Adherence will be assessed at each of the follow up visits by pill counts and patient medication diaries. Medications will only be available from the Investigational Drug Service (IDS), thus an accurate assessment of medication dispensed will be available. Subjects will be instructed to return unused medications at each visit. By pill count, medication adherence will be assessed. Adherence will be defined as intake of > 80% of the prescribed CBZ or placebo – persistent nonadherence to the study regimen may lead to discontinuation of the study for those subjects. For patients receiving CBZ, adherence will also be assessed by measuring trough CBZ levels at each visit. It is expected that the levels will be between 4 and 12 µg/ml. Standard deviations of sequential levels will also be used as a measure of adherence (46).

End of treatment assessment (week 52 visit + 1 wk):

Hepatic venous pressure gradient – see above

Liver biopsy – see above

Concomitant Medications:

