Hyponatremia can occur in patients with chronic liver disease and chronic diuretic use in the management of ascites. Therefore, its presence may reflect the natural course of liver disease. On rare occasion, inappropriate antidiuretic hormone (ADH) secretion has been associated with CBZ. Serum electrolytes will be monitored regularly as well as a “first void” urinalysis to assess specific gravity (see appended Study Flow Chart). Alterations or thyroid function studies have been reported with CBZ treatment, but they have not been associated with clinical evidence of hypothyroidism. T4 and TSH will be monitored periodically (see Study Flow Chart in Appendix 2).

Suicide

An increase in suicide in patients taking CBZ has been reported in one study (24) but numerous other studies provide strong evidence against this potential risk (25-29). Nevertheless we will monitor for suicidal tendencies very assiduously and patients will be withdrawn based on well-established guidelines (see above).

Pregnancy

Transplacental passage of CBZ to the fetus is rapid and associated with congenital malformations, including spina bifida, cardiovascular malformations, and developmental disorders.

Patients will be asked to practice effective birth control while they are taking CBZ in this study. However, given the long duration of therapy and the number of female subjects in the child-bearing age, the following precautions will be taken:

1. All female subjects of child-bearing age will undergo urine pregnancy test on enrollment, prior to starting therapy, and monthly during the trial.
2. All female subjects of child-bearing age will need to use a barrier method of contraception as CBZ has the potential to interfere with oral contraceptives
3. All female subjects of child-bearing age will be counseled monthly during the treatment portion of the trial on barrier methods of birth control.
4. If a subject is found to be pregnant, CBZ will be immediately discontinued and permanently stopped and the subject will be referred to an obstetrician for advice and consultation
5. The study will collect data on the outcomes of any pregnancies that occur in women who conceived while taking the study medication.
6. The study will collect data on the outcome of liver disease for those women whose medication was immediately discontinued.

Breast feeding

A Preliminary Study of the Efficacy and Safety of Carbamazepine in Severe Liver Disease Due to Alpha-1 Antitrypsin Deficiency

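### Monthly pregnancy testing is promised in the Pregnancy subsection, but the visit schedule ties the test to visits that leave 7 of 12 treatment months without one

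*Combined protocol and SAP*

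**What the plan says.** The Pregnancy subsection, under Screening and management for specific adverse events, gives a numbered list of precautions. The first is: "All female subjects of child-bearing age will undergo urine pregnancy test on enrollment, prior to starting therapy, and monthly during the trial". The third is that these subjects "will be counseled monthly during the treatment portion of the trial on barrier methods of birth control". The subsection justifies the precautions by the length of treatment and the number of women who could conceive. It requires a barrier method because the drug may interfere with oral contraceptives.

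The On-treatment assessments section gives a frequency for the same test. Female subjects of child-bearing age "will undergo a urine pregnancy test on visit S2, enrollment, and at each follow up visit during the trial". The paragraph also fixes the visits: "Study visits will be scheduled at weeks 4 (+/- 1 week), 8 (+/- 2 weeks), 18 (+/- 2 weeks), 36 (+/- 2 weeks", with a last one at week 52a (up to 3 weeks later). Efforts to ensure adherence to the protocol repeats the schedule: "18 weeks (+/- 2 weeks), 36 weeks (+/-2 weeks) and finally at the week 52 visit(+3 weeks".

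Three other statements bear on the count:
- On-treatment assessments plans no further invasive testing "until the week 52b visit when a repeat liver biopsy and HVPg will be obtained".
- Study design describes MELD scoring as "including measuring at 7 follow-up visits while on active medication or placebo", although the schedule lists five follow-up visits.
- On-treatment assessments allows extra visits at the investigator's discretion, and then adds: "Full list of assessments can be found on the schedule of events flow sheet".

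**The concern.** Two parts of one protocol give different frequencies for the same safety test. Staff who plan from the visit paragraph would test less often than the Pregnancy subsection promises.

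The protocol's Safety text on carbamazepine says the drug can harm the fetus, and the Pregnancy subsection names spina bifida, cardiovascular malformations and developmental disorders. A pregnancy requires immediate and permanent discontinuation, and that rule works only if the pregnancy is detected. Monthly testing and monthly counseling are two of the stated safeguards, alongside the barrier method.

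The readable text offers no other checkpoint. The Randomization section has the pharmacy supply drug to last until the next visit plus 5 days, by courier to the home, and does not tie supply to a negative test. Nothing here touches the efficacy analysis, power or type I error.

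**Working it through.** The plan gives no figure of its own to reproduce. The check is a count of months with a scheduled test.

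**Inputs**
- Treatment lasts 12 months, taken as 52 weeks (Study design).
- Follow-up visits are at weeks 4, 8, 18, 36 and 52a (On-treatment assessments; Efforts to ensure adherence to the protocol).
- One month is 52/12 = 4.33 weeks. This is my convention, because the protocol does not define a month.
- The enrollment test is left out of the monthly count, because the Pregnancy subsection lists it separately.

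**Month of each visit** = week divided by 4.33, rounded up. **Gap** = weeks since the previous scheduled test, with enrollment at week 0.

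| Visit week | Week / 4.33 | Month | Gap (weeks) |
|---|---|---|---|
| 4 | 0.92 | 1 | 4 |
| 8 | 1.85 | 2 | 4 |
| 18 | 4.15 | 5 | 10 |
| 36 | 8.31 | 9 | 18 |
| 52 | 12.00 | 12 | 16 |

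Months 1, 2, 5, 9 and 12 have a test. Months 3, 4, 6, 7, 8, 10 and 11 do not: 12 - 5 = 7. The first two months match the monthly rule. The shortfall is all in months 3 to 12, where 3 of 10 months have a listed visit.

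**Does the answer depend on the convention?**
- *Visit windows.* The windows are weeks 3-5, 6-10, 16-20, 34-38 and 52-55. Across all positions the empty months run from 7 to 9. The 9 needs the first two visits to share month 2 and the last to fall after month 12. The widest possible gap is 38 - 16 = 22 weeks.
- *Enrollment test counted as month 1.* Still 7 at nominal timing, because week 4 already covers month 1; 6 to 8 across the windows.
- *28-day months, enrollment test not counted.* 8 or 9 empty at nominal timing, depending on whether the year is cut into 12 or 13 and on how edges are treated.
- *Week 52b counted as a separate visit.* It adds no month that week 52a does not cover.

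No reasonable definition of a month makes the listed visits monthly.

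**Can the discretionary visits close the gap?** Their described content is history, depression and suicide assessment, biochemistry and drug level, with an optional physical examination. A pregnancy test is not named. Even if the rule for each follow-up visit is read to include them, they are optional and do not guarantee a test in any given month.

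**The case against.** The best defense is that the two rules are compatible. The Pregnancy subsection is current and mandatory. The visit paragraph says which visits include a test and does not say that testing happens only there. A site that obeys both tests monthly and also at visits. This stands. A reader might infer from the count that the protocol leaves women untested for 7 months of the year. The documents do not support that: the months lack a scheduled visit, but the monthly rule still applies in them. The shortfall arises only where staff work from the visit paragraph alone.

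The second defense is that the flow chart is said to hold the full list of assessments, and that manuals of operations are to be prepared (Statistical Support, Data Management and Quality Control). Neither was available, and either may name monthly tests or calls. This also stands, so it cannot be said that the plan has no monthly mechanism. It does not remove the difference between the two passages of text.

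Third, the seven follow-up visits mentioned in Study design might suggest better coverage. No readable schedule places seven visits after enrollment. The five listed visits reach seven only if enrollment and week 52b are both added, and neither covers a mid-year month.

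Finally, the exposure is limited. Twenty subjects receive the drug, the number of women who could conceive is not given, and barrier contraception is mandatory. That argues for a modest fix but does not justify leaving the texts apart.

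**Conclusion.** The inconsistency is real and should be fixed. The Pregnancy subsection requires a monthly test and monthly counseling; the visit section schedules the test at five follow-up visits. Testing by the visit section alone misses 7 of 12 months at nominal timing and leaves gaps of 10, 18 and 16 weeks after week 8. The count assumes twelve equal months in 52 weeks and visits on their nominal dates.

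The conclusion is limited to the readable text. That text does not say how testing between visits happens, and the flow chart may. The visit paragraph covers only the test; monthly counseling could be done by telephone, but no such contact is named. The matter concerns participant safety and consistency, not inference about the drug's effect.

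**What to change.** 1. Check the flow chart and any manual of operations for monthly tests and contacts between visits.
2. Keep the monthly rule of the Pregnancy subsection. Amend On-treatment assessments so that the test is due at visit S2, at enrollment, at every follow-up visit, and monthly between visits. Change the flow chart too if it shows visits only.
3. Name the route for months without a visit: a home or local urine test with a documented result, and a call for the barrier-contraception counseling. A remote route is needed in practice, since Reimbursement of subjects plans for participants living more than 1,300 miles away.

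If the flow chart already schedules this, only the visit paragraph needs aligning. The difference should not be settled by testing at visits only, because that would withdraw a safeguard the protocol already promises.

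The cost is one amended sentence, a flow-chart check, and about 12 - 5 = 7 extra urine tests and 7 calls per woman of child-bearing age. The monthly rule already implies those tests and calls. No total for the trial can be given, because the documents do not state how many such women are expected.
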